8.3 Analysis Populations

The primary efficacy population will be the Full Analysis Set (FAS) that will include all randomized and treated subjects. Following the intent-to-treat philosophy, subjects will be analyzed within the treatment group to which they are randomized.

The primary safety population will be all treated subjects. For safety analyses, subjects will be classified based upon the treatment received.

8.4 Subject Disposition

An accounting of all randomized subjects by disposition will be presented. Subjects who discontinue study drug prematurely or withdraw from the study will be summarized and listed, with a description of the reason for early termination/withdrawal.

8.5 Subject Characteristics

Demographic and other baseline characteristics will be summarized.

8.6 Concomitant Medications

Concomitant medications will be coded by the World Health Organization (WHO) Drug Dictionary to Anatomical Therapeutic Classification (ATC) and preferred drug name. Concomitant medications will be summarized by ATC level and preferred drug name and listed.

8.7 Treatment Compliance and Extent of Exposure

Compliance with study drug dosing will be recorded within the eDiary. From these entries, summaries of treatment compliance and exposure will be produced.

8.8 Efficacy Analyses

The efficacy endpoints will be summarized within the FAS using descriptive statistics by time point and treatment. For the WI-NRS and AI-NRS endpoints (change from baseline, 3-point and 4-point responders) results will be summarized at the primary time point, Week 6, as well as at Week 2 and 4. The WI-NRS and AI-NRS results will be summarized at baseline and Weeks 2, 4 and 6. For each of these measures the result at a time point are based upon the average of the results leading up to that time point. The night-time scratching events, ItchyQoL, 5-D Pruritus Scale and sPGA will also be summarized at baseline and Weeks 2, 4 and 6 with change from baseline summarized at Weeks 2, 4 and 6. Week 6 is the primary time point for the ItchyQoL. The PGIC will be summarized at Weeks 2, 4 and 6.

For the primary and key secondary endpoints these statistics will include 95% confidence intervals for the treatment difference. Testing will also be used for the primary and key secondary endpoints.

For the responder rate endpoints subjects will be considered a responder if they have at least a 3 or 4 point reduction in WI-NRS / AI-NRS between baseline and the corresponding week.

The difference in the primary efficacy outcome measure (WI-NRS change from baseline to Week 6) between treatment groups will be tested using an analysis of variance (ANOVA) model controlling for the stratification factors. A main effects model with an interaction term (treatment by stratification factors) and a Type II hypothesis will be used. More precisely this ANOVA model uses the following as a stratified adjusted measure of the change from baseline for a given treatment group:

$$\Delta = \sum_{j=1}^4 \frac{n_{1j}n_{2j}}{n_{1j}+n_{2j}} \Delta_j,$$

where j represents the stratification cells, n is the sample size for treatment 1 and 2 and Δ_j is the change measures for stratum j .

Conceptually the hypotheses being tested are:

$$H_0: \Delta_{Placebo} \geq \Delta_{Serlopitant} \qquad H_a: \Delta_{Placebo} < \Delta_{Serlopitant}$$

where $\Delta_{Placebo}$ is the placebo change from baseline and $\Delta_{Serlopitant}$ is the similar measure for serlopitant. Each serlopitant treatment group (1 mg and 5 mg) will be compared to placebo separately.

The primary endpoint will utilize the imputation methods as outlined in [Section 8.2](#). Sensitivity analyses in which Last Observation Carried Forward, LOCF, and Baseline Observation Carried Forward, BOCF, are used will be performed. The LOCF approach assumes subject's final assessment is reflective of their future assessment and can be useful if

subjects are withdrawing due to lack of efficacy, as this lack of efficacy is carried forward. The BOCF approach for responder rate endpoints is equivalent to a missing equals failure imputation.

The differences between treatment groups for the ItchyQoL key secondary endpoint will be tested using the same analysis of variance (ANOVA) model used for the primary endpoint. A Cochran Mantel Haenszel (CMH) test controlling for the ‘as randomized’ stratification factors will be used for the responder rate key secondary endpoint.

8.9 Psychometric Analyses

A psychometric assessment of the WI-NRS will be conducted to assess test-retest reliability, construct validity and responsiveness. These will be conducted outside of the statistical analysis plan for this study and will include analyses of: intra-class correlation coefficients (ICC), Pearson’s correlations, and change scores for test-retest reliability; Pearson Product Moment or Spearman Correlations for concurrent validity; t-test analyses or ANOVA for known groups validity; and correlations of change scores for WI-NRS and other measures for responsiveness. In addition, a responder definition will be explored using anchor- and distribution-based methods.

8.10 Safety Analyses

8.10.1 Adverse Events

The incidence of all AEs and treatment-related AEs will be tabulated by treatment received. These AEs will be classified by system organ class and preferred term using the Medical Dictionary for Regulatory Activities (MedDRA). For incidence reporting, if a subject reported more than one AE that was coded to the same system organ class or preferred term, the subject will be counted only once for that specific system organ class or preferred term. An overview of AEs, which includes subject incidence of AEs, treatment-related AEs, AEs by severity, SAEs, deaths, and AEs leading to discontinuation, will be presented.

SAEs will be listed and summarized in a similar manner to AEs.

8.10.2 Clinical Safety Laboratory Results

Clinical safety laboratory values will be measured by a central laboratory. Summary statistics for actual values and for changes from baseline will be tabulated for laboratory results by scheduled visit. Graphs of laboratory values over time will also be produced.

Subjects with clinical laboratory values outside of the normal reference range at any post-baseline assessment will be summarized. Shifts from baseline laboratory values will be tabulated.

8.10.3 Vital Signs

The observed data and change from baseline for each measurement day will be summarized with descriptive statistics.

8.10.4 *Electrocardiograms*

The overall ECG assessment (abnormal or normal) will be summarized along with a summary of how many subjects developed a post treatment abnormal result. The study relevance of the finding will be provided in a listing.

8.11 *Interim Analyses*

This study includes an iDMC that will review study results to identify potential safety concerns. The iDMC is not tasked with stopping the study early for efficacy or for futility determinations.

8.12 *Pharmacokinetics Data*

The PK data and analysis for serlopitant and metabolites will be reported in a PK report that will be a part of the clinical study report.

9 *ADMINISTRATIVE ASPECTS*

9.1 *Changes to the Protocol*

Protocol amendments must be made only with the prior written approval of the Sponsor. An investigator signature will be obtained for the initial protocol and any amendments. Substantial amendments will be provided to the appropriate regulatory authorities. No protocol changes affecting the following will be made without the written approval of the Sponsor and the responsible IRB or EC:

- Safety and/or eligibility of subjects
- Data integrity
- Study design or conduct
- Willingness of a subject to participate in the study

9.2 *Study Termination*

The Sponsor has the right to terminate this study at any time. Reasons may include, but are not limited to, evidence of a potential safety risk in this study or other serlopitant studies or poor enrollment, or the recommendation of the iDMC. A written statement fully documenting the reasons for study termination will be provided to the IRB or EC.

9.3 *Monitoring and Auditing Procedures*

The Sponsor will designate study monitors who will be responsible for monitoring the conduct of this study. A separate study Monitoring Plan will include details regarding the responsibilities of the study monitors, investigator responsibilities in providing access to records and addressing issues identified, the frequency and structure of monitoring visits, and adherence to subject confidentiality as outlined in the Informed Consent Form (ICF).

9.4 Transfer of Obligations

The Sponsor will delegate certain aspects of study oversight to Contract Research Organizations (CROs). The specific responsibilities will be detailed in Transfer of Obligations documents.

9.5 Informed Consent

The purpose of the study, the procedures to be carried out, and any potential risks of study participation will be described in non-technical terms in the ICF. After having reviewed and understood the ICF, subjects will be required to read, sign, and date an IRB-approved or EC-approved consent form before any study-specific procedures are carried out. Subjects below the legal age of consent will be required to read, sign, and date an IRB-approved or EC-approved assent form, and his/her parent(s)/guardian(s) will be required to read, sign, and date an IRB-approved or EC-approved consent form. Subjects will be assured that they may withdraw from the study at any time without jeopardizing medical care related to or required as a result of study participation. The original signed consent and assent forms will be maintained in the investigator site file. Copies of signed consent/assent forms will be provided to the subject.

9.6 Communication with the Institutional Review Board or Ethics Committee

The IRB or EC is constituted and operates in accordance with the principles and requirements described in the ICH E6 guideline. The protocol, informed consent/assent form, other written subject information, and any proposed study advertising material must be submitted to the IRB or EC for written approval. IRB or EC approval of these documents will be provided to the investigator. The study will not start until the IRB or EC has granted its approval of the study materials and procedures.

Protocol amendments will be submitted to the IRB or EC as explained in [Section 9.1](#). SAE information will be submitted to the IRB or EC as explained in [Section 7.4](#).

If the study is terminated by the Sponsor, a written statement fully documenting the reason(s) for study termination will be provided to the IRB or EC.

9.7 Disclosure and Confidentiality

By signing this protocol, the investigator agrees to keep all information provided by the Sponsor in strict confidence and to require the same confidentiality from site staff and the IRB or EC. Study documents provided by the Sponsor (e.g. protocol, IB, eCRFs) will be stored appropriately to ensure their confidentiality. The information provided by the Sponsor to the investigator may not be disclosed to others without direct written authorization from the Sponsor, except to the extent necessary to obtain informed consent/assent from subjects who wish to participate in the study.

The investigator must ensure that the subjects be identified by a unique subject study number. Other study-related documents that may contain confidential participant information

(e.g. signed ICFs) will be kept in strict confidence by the investigator and be stored in a secure location with access restricted to the study staff.

9.8 Records and Electronic Case Report Forms

All study data except central laboratory, PK, eDiary, actigraphy, and ECG data will be recorded in an eCRF system. Data will be entered at the site by the appropriately designated and trained site personnel. All source documents from which eCRF entries are derived should be placed in the subject's medical records. eCRFs will be completed for every subject screened in the study.

The study monitor will review all eCRFs in detail and will have access to participant medical records, laboratory data, and other source documentation to allow required eCRF fields to be verified by source data.

Data consistency and plausibility checks against data entered into the eCRF will be included in the eCRF system. Data corrections can be performed in the eCRFs by the site. For each instance of data modification, the system requires a reason for change. The system keeps a full audit trail of the data values, the date and time of modification, and the electronic signature of the user who performed the change.

After a full review of the eCRFs by the study monitor and resolution of any data clarifications, the investigator will review, sign, and approve the subject's eCRF. All essential documents, source data, clinical records, and laboratory data will be retained by the site in accordance with the ICH E6 guideline and the site's data retention policies. These records must be available for inspection by the Sponsor, monitor, and regulatory authorities.

Further detail regarding data management and eCRFs is included in the Data Management Plan.

9.9 Good Clinical Practices and Ethical Study Conduct

The study procedures outlined in this protocol will be conducted in accordance with applicable ICH Guidelines, including ICH E6: Good Clinical Practices. As this study is conducted under a US IND, the investigator will also ensure that the basic principles of "Good Clinical Practice", as outlined in 21 CFR 312, subpart D, "Responsibilities of Sponsors and Investigators", 21 CFR, part 50 and 21 CFR, part 56 are adhered to.

The study procedures outlined in this protocol will also be conducted in accordance with the principles of the Declaration of Helsinki.

9.10 End of Study Notification

The Sponsor will notify appropriate regulatory authorities and the IRB within 90 days from the end of the clinical study. The end of the clinical study is defined as the last study visit for the last subject.

9.11 Publication of Results

All publications (e.g. manuscripts, abstracts, oral/slide presentations, book chapters) based on this study or relying on data from this study must be submitted to the Sponsor for review and release before submission for publication. The Sponsor is responsible for final approval of all publications.

9.12 Final Report

A clinical trial summary report will be provided to the appropriate regulatory authorities within one year of the end of the clinical study.

APPENDIX A SCHEDULE OF ACTIVITIES AND ASSESSMENTS

Table 2 Schedule of Visit Activities

Examination	Consent	Screening	Baseline	Week 1	Week 2	Week 4	Week 6	ETD*	F/U**	Comments & Clarifications
Study Days (D)			D 1	D 8	D 15	D 29	D 43	*	**	
Visit Window in Days (d)			-2d, +3 d	±3 d	±2 d	±3 d	±3 d	*	±3 d	
Informed consent/assent	X									Informed consent will occur prior to any protocol-mandated procedures, including the stopping of any excluded therapies. This may occur prior to the initial Screening visit.
Medical history		X								
I/E criteria		X	X							
Randomization			X							
Physical exam		X			X		X	X	X	Screening physical exam is complete; other exams are targeted
Vital signs		X	X		X	X	X	X	X	Height will be assessed at screening; Weight will be assessed at screening, baseline, Week 2, Week 6, ETD, and F/U
ECG		X			X				X	
Labs		X			X		X	X	X	Screening labs, including urine pregnancy test, may be collected during the screening period (after Screening visit but prior to the Baseline visit); Endocrine and cardiac, and reproductive endocrine labs will be collected at screening, Week 6, ETD, and F/U
PK					X	X	X	X		
IGA-AD		X	X		X	X	X	X	X	
5-D Pruritus Scale		X	X		X	X	X	X	X	
Dispense study drug			X		X	X				
Collect study drug					X	X	X	X		
Concomitant medications			X	X	X	X	X	X	X	
AEs			X	X	X	X	X	X	X	After informed consent/assent, but prior to study drug administration, only SAEs caused by a protocol-mandated intervention will be collected

* Early Treatment Discontinuation (ETD) visit occurs within 7 days of last dose for subjects who discontinue study drug treatment prior to the Week 6 visit

**The Follow-up (F/U) visit occurs 28 days (± 3 days) after the Week 6 visit (Study Day 68-74) or the ETD visit (for subjects who discontinue study drug early). Subjects who discontinue study drug prior to Study Day 15 should have a follow-up visit 6 weeks (± 3 days) after randomization (Study Day 40-46) so that all randomized subjects will have a Week 6 evaluation.

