4. Average weekly WI-NRS score ≥ 6 for each week of the screening period, as recorded in the eDiary.
5. Diagnosis of atopic dermatitis, as defined by the 2014 American Academy of Dermatology (AAD) Guidelines of Care for the Management of Atopic Dermatitis.¹
 - a. Subjects with active atopic dermatitis skin involvement must have had stable skin disease, defined as experiencing no disease flares, for at least 4 weeks immediately prior to randomization. Subjects using stable doses of bland emollients, topical calcineurin inhibitors, and/or low- to mid-potency topical corticosteroids at the initial Screening visit must be willing to continue these at the same doses and frequencies throughout the study.
 - b. Subjects without active atopic dermatitis skin involvement must have had a past diagnosis of atopic dermatitis, supported by written records documenting the presence of features consistent with the 2014 AAD Guidelines.
6. All female subjects who are of childbearing potential must practice highly effective contraception (i.e., pregnancy prevention method with a failure rate of $< 1\%$ per year) from the time of the initial Screening visit until 4 weeks after last dose of study drug. All fertile male subjects, with partners who are females of childbearing potential, must use condoms from randomization until 4 weeks after last dose of study drug. All subjects who are fertile males or females of childbearing potential must also refrain from sperm/egg donation starting from first dose of study drug and until 4 weeks after last dose of study drug. Please refer to [Section 7.1.5](#) for acceptable methods of contraception.
7. Weight ≥ 32 kg at the baseline visit.
8. Willing and able to complete once-daily eDiary entries within a consistent timeframe for the duration of the study.
 - a. Subjects must have $\geq 80\%$ eDiary completion rate during the screening period.
9. Judged to be in good health in the investigator's opinion.

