12. Treatment with any investigational therapy within 4 weeks prior to randomization.
13. Allergen immunotherapy within 6 months prior to randomization.
14. Serum creatinine, total bilirubin, ALT or AST > 2x the upper limit of normal (ULN) during screening.
15. History of malignancy within 5 years prior to randomization, with the exception of completely treated and non-metastatic basal cell carcinoma or squamous cell carcinoma of the skin.
16. History of a major psychiatric condition (including major depressive disorder, bipolar disorder, or schizophrenia), suicidal ideation, or suicide attempt.
17. Known active hepatitis infection.
18. Known history of human immunodeficiency virus (HIV) infection.

19. Documented history of parasitic infection, including skin parasites such as scabies, within 12 months prior to randomization.
20. Known active parasitic infection.
21. Regular long-distance running (e.g. 10Ks, marathons) or long-distance bicycling (e.g. 30 + miles) and/or strenuous physical activity (e.g. bodybuilding) within 2 weeks prior to randomization
22. Presence of any medical condition or disability that, in the investigator's opinion, could interfere with the assessment of safety or efficacy in this trial or compromise the safety of the subject, including clinically significant ECG abnormalities during screening.
23. History of hypersensitivity to serlopitant or any of its components.
24. Currently pregnant or breastfeeding, or male subject with a pregnant or breastfeeding partner
25. Females of childbearing potential who are unable or unwilling to practice highly effective contraception (pregnancy prevention); fertile male subjects who are unable or unwilling to use condoms with female partners of childbearing potential.

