6.5.1 Informed Consent/Assent

Informed consent will occur prior to any protocol-mandated procedures, including the stopping of any excluded therapies. This may occur prior to the initial Screening visit.

6.5.2 *Screening Visit/Period*

An initial Screening visit should be scheduled to occur 14 days (-2 days, +3 days) prior to the Baseline visit. The following screening procedures are to be performed at the initial Screening visit:

- Inclusion/exclusion criteria review
- Medical history
- Complete physical examination
- Vital signs (including height and weight)
- IGA-AD
- 5-D Pruritus Scale
- ECG
- Schedule the baseline visit
- Provide actigraphy device with instructions
- Provide eDiary with instructions

During the screening period (after consent/assent and prior to the baseline visit), the following screening procedure is to be performed:

- Laboratory
 - Reproductive endocrine labs for females
 - Urine pregnancy test for females of childbearing potential (with positive or equivocal results confirmed by a serum pregnancy test)
 - Endocrine and cardiac
 - Hematology
 - Chemistry
 - Urinalysis

6.5.3 *Baseline Visit*

The Baseline visit occurs 14 days (-2 days, +3 days) after the Screening visit. At the Baseline visit, the following procedures and assessments are to be performed:

- Inclusion/exclusion criteria review
- Vital signs

- IGA-AD
- 5-D Pruritus Scale
- Concomitant medications
- AEs
- Randomization if eligible
- Dispense study drug
- Schedule future visits

Randomized subjects will begin treatment with study drug in the evening of the Baseline visit (Study Day 1).

6.5.4 *Week 1 Visit*

The Week 1 visit is a telephone visit that occurs 7 days (± 3 days) after the Baseline visit (Study Day 5-11). At the Week 1 visit, the following procedures and assessments are to be performed:

- Concomitant medications
- AEs

6.5.5 *Week 2 Visit*

The Week 2 visit occurs 14 days (± 2 days) after the Baseline visit (Study Day 13-17). At the Week 2 visit, the following procedures and assessments are to be performed:

- Vital signs (including weight)
- IGA-AD
- 5-D Pruritus Scale
- Targeted physical examination
- ECG
- Laboratory
 - Urine pregnancy test for females of childbearing potential (with positive or equivocal results confirmed by a serum pregnancy test)
 - Hematology

- Chemistry
- Urinalysis
- PK blood sample collection
- Concomitant medications
- AEs
- Collect returned study drug
- Dispense study drug

6.5.6 *Week 4 Visit*

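### No pregnancy test is scheduled at Baseline, so Exclusion 24 is judged at randomisation on a urine test that can be up to 17 days old, and Section 6.5.2 and Table 2 disagree on its earliest date

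*Protocol*

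**What the plan says.** Protocol Section 4.3, Exclusion 24, excludes "Currently pregnant or breastfeeding, or male subject with a pregnant or breastfeeding partner". Section 6.5.3 and Table 2 repeat the inclusion/exclusion review at Baseline. The same visit contains randomisation and dispensing, and the first dose is taken that evening (Study Day 1).

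The scheduled pregnancy test before dosing is one of the screening laboratory items in Section 6.5.2: "Urine pregnancy test for females of childbearing potential (with positive or equivocal results confirmed by a serum pregnancy test"). Its timing is given twice:

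- Appendix A, Table 2, comment on Labs: "Screening labs, including urine pregnancy test, may be collected during the screening period (after Screening visit but prior to the Baseline visit").
- Section 6.5.2: "During the screening period (after consent/assent and prior to the baseline visit), the following screening procedure is to be performed".

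On consent, Section 6.5.1 adds: "This may occur prior to the initial Screening visit".

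The Baseline procedure list in Section 6.5.3 has no laboratory item. The Labs row is blank at Baseline in both Protocol Table 2 and SAP Table 2. On spacing, Section 6.5.3 states: "The Baseline visit occurs 14 days (-2 days, +3 days) after the Screening visit". The next scheduled pregnancy test is at the Week 2 visit (Section 6.5.5).

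Inclusion 6 requires highly effective contraception in females of childbearing potential "from the time of the initial Screening visit until 4 weeks after last dose of study drug".

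**The concern.** The eligibility decision and the evidence for it fall on different days. Exclusion 24 concerns a current state and is reviewed on the day of dosing, but the schedule supplies no result from that day. Both timing rules place the test before the Baseline visit.

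An early test is the weakest case. A sample taken at the Screening visit follows a period in which the protocol required no contraception, so a negative urine result may miss a conception shortly before it. A site that follows the schedule exactly could then randomise and dose a subject who already meets Exclusion 24.

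The stake is subject safety, in a trial open from age 13. There is also an operational cost: pregnancy ends study drug treatment under Section 5.6, and Section 7.1.5 requires it to be reported and followed to its outcome.

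**Working it through.** **Inputs (protocol)**

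- Screening to Baseline: 14 days, -2/+3 (Sections 6.5.2 and 6.5.3).
- Week 2 visit: 14 days ±2 after Baseline (Section 6.5.5).
- Dosing: 3 tablets at bedtime on Day 1, then one each bedtime (Section 5.3).
- Study day at a visit = days after Baseline + 1.

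**Step 1. The plan's own figure.** The Week 2 visit falls 14 - 2 = 12 to 14 + 2 = 16 days after Baseline. Adding 1 gives Study Day 13 to 17, as Section 6.5.5 states.

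**Step 2. Screening to Baseline.** 14 - 2 = 12 days to 14 + 3 = 17 days.

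**Step 3. Age of the result at first dose, under Table 2.**

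- Latest permitted test, the day before Baseline: 1 day.
- Earliest test, on the day of the Screening visit (the Labs row is marked in that column): 12 days at the shortest interval, 17 at the longest.
- Range: 1 to 17 days. Seventeen is the worst case, not the typical value.

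**Step 4. Time between the pre-dose test and the Week 2 test.** Gap = age at Baseline + days from Baseline to Week 2.

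| Pre-dose test taken | Shortest gap | Longest gap |
|---|---|---|
| Day before Baseline | 1 + 12 = 13 days | 1 + 16 = 17 days |
| At the Screening visit | 12 + 12 = 24 days | 17 + 16 = 33 days |

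The permitted range is therefore about 13 to 33 days.

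**Step 5. Tablets taken before the Week 2 test.** Assume full compliance and a daytime visit. If the visit is 12 days after Baseline, the count is 3 + 11 (Days 2 to 12) = 14. If it is 16 days after, the count is 3 + 15 (Days 2 to 16) = 18.

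**Step 6. The two timing rules side by side.** Table 2 opens the window after the Screening visit. Section 6.5.2 opens it after consent or assent, and Section 6.5.1 lets consent come before Screening. Table 2 therefore implies a maximum age of 17 days, while the parenthesis in Section 6.5.2 states no explicit maximum. The two are not the same rule.

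**The case against.** The strongest reply has four parts.

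1. **Safeguards exist.** The criteria are reviewed again at Baseline, contraception is required from Screening (12 to 17 days before dosing), and Section 6.2.3 allows samples at unscheduled visits when clinically indicated. This stands as mitigation and makes the event unlikely. None of the three requires a current test result before the first dose.

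2. **No rule is broken.** Exclusion 24 names no test and no date, and the pregnancy-testing recommendations in the reference list are not available here. This stands too: the point is a mismatch between a criterion and its schedule, not a breach of a stated standard.

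3. **A Baseline urine test would also miss a very recent conception.** True. It would, however, come after 12 to 17 days of required contraception, whereas a test at Screening comes after none. The limitation is reduced, not removed.

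4. **The screening test may well be recent.** It may be taken the day before Baseline, and the gap to Week 2 can be as short as 13 days. This is why the full range is shown.

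A reader might also infer from Section 6.5.2 that the test could be far older than 17 days, for example taken at consent before a long washout of a biologic. The documents do not support that as a finding. The sentence in Section 6.5.2 opens with the screening period, which Section 3.1 sets at 2 weeks, so the reference to consent can be read as an ordering condition within that period. Section 6.2.3 sends laboratory timing to Appendix A, where Table 2 starts the window after the Screening visit. No passage describes a test taken during a washout. What remains is a conflict of wording.

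**Conclusion.** The point holds as a gap in the schedule. Under Table 2, the only scheduled pre-dose pregnancy result can be 1 to 17 days old at first dose, no test is scheduled at Baseline, and the next comes about 13 to 33 days after the first, with 14 to 18 tablets taken by then. Separately, Section 6.5.2 and Table 2 conflict on the earliest test date.

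A reader might conclude that the plan leads to pregnant subjects being dosed. The documents show only that the schedule does not rule it out. They give no pregnancy rate, so the number affected cannot be estimated; that it is small is an assumption. The tablet counts assume full compliance. Nothing here bears on the efficacy analysis. The case for acting rests on a serious possible consequence and a low cost of correction.

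**What to change.** Reconcile Exclusion 24, Sections 6.5.2 and 6.5.3 and Appendix A, Table 2 so that the Baseline eligibility review rests on a current pregnancy result. One way is to align the local urine test that is already required with the Baseline visit, before randomisation, and to show it in Section 6.5.3 and in the Baseline column of Table 2. State one timing rule for this test in both Section 6.5.2 and Table 2, and carry any change into SAP Table 2. The choice of rule is for the sponsor; the passages need to agree.

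The cost is amendment wording. If the existing test is moved rather than a second one added, there is no extra procedure, but some subjects would be screened out later than now. An equivocal result would hold up randomisation until the central laboratory reports the confirmatory serum test.
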